Several considerations led to the selection of the progestin. Concern has been raised that the addition of a progestin may diminish the putative cardiovascular benefits of estrogen replacement therapy. Progestins alone tend to raise LDL and lower HDL cholesterol levels. In the PEPI trial, all hormone regimens lowered LDL cholesterol levels, but medroxyprogesterone acetate (MPA) significantly attenuated the estrogen related increase in HDL cholesterol levels. Oral micronized progesterone in doses of 1 and 2 mg appeared to have the least detrimental effect on plasma lipoprotein levels. However there is little safety information on the long-term use of continuous micronized progesterone. The Nurses Health Study data suggests that the addition of progestin does not appear to attenuate the cardioprotective effects of post menopausal estrogen use. The choice of MPA will also allow for it to be combined in a single capsule with the CEE selected. By reducing the number of daily capsules that each woman with a uterus will have to take, compliance in the HRT arm of the trial should be increased.

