5. MASKING

To promote uniform follow-up of all trial participants, all randomized women and clinical center personnel responsible for randomization and follow-up will, to the extent possible, remain masked to treatment assignments until the end of the trial. This will increase the probability that all women will receive similar concomitant treatments, testing and evaluation during the conduct of the trial. It is likely however that due to the occurrence of side effects, some women and/or clinical personnel will assume knowledge of one of their treatment assignments. Women will be instructed to not discuss gynecological issues with WAVE cardiology staff. Rather, each center will have a study gynecologist, or designated personnel to whom women can address concerns about side effects.

Each woman with a uterus will be asked to fill out a bleeding diary for the first six months following randomization. The diary will be returned to the gynecology staff. After review of the entries at the first six month visit, a decision by the OB/GYN physician will be made as to whether or not the diary may be discontinued.

Personnel at the central angiographic laboratory and the central biochemistry laboratory, will also be masked to treatment assignments. This will permit unbiased assessments of the trial's primary and secondary outcomes.

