8.4 MONITORING POTENTIAL HORMONE REPLACEMENT THERAPY SIDE EFFECTS

8.4.1 Symptomatic Management

Women will be instructed on palliative management of symptoms such as breast tenderness or bloating. The management of these side effects includes dietary changes, use of a mild diuretic for fluid retention, vaginal lubricants and reassurance. If these symptoms continue and are not tolerated, the dose of study hormone drug will be reduced in frequency to 5 days per week or less and then slowly increased to attempt to achieve the protocol dosing regimen.

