18.2 PRIMARY ENDPOINT

- To examine the chronic effect of study drug on changes in perfusion defect size (ischemic burden) from baseline to three year perfusion stress test.

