18.4 SUBSTUDY PROTOCOL

- All women randomized to participation in the overall trial will be asked to participate in this substudy.
- Women will undergo exercise gated SPECT imaging within 7 days of randomization and prior to initiation of study drug. The exercise protocol will include use of a standard Bruce

protocol with gated SPECT myocardial perfusion imaging. Technetium 99 tomography will be performed at rest and following exercise with reinjection performed in patients with fixed defects.

- At three months, during one of their follow up visits, women will undergo repeat exercise treadmill test. For those women who had perfusion defects initially, a follow up gated SPECT perfusion image will also be obtained at this time point. Those women with negative perfusion scans at enrollment will undergo only exercise ECG testing at the three month time point.
- At completion of the protocol and prior to 3 year recatheterization, all women will undergo repeat Bruce treadmill testing and gated SPECT perfusion imaging. (see Figure 1)

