18.6 DATA ANALYSIS

The goal of this analysis is to examine the acute and chronic effects of hormone replacement therapy and antioxidants on direct vascular tone, ischemia, and treadmill variables using stress myocardial perfusion and function imaging. Each woman's perfusion defect size will be quantified as a percentage of the total area on a bulls eye plot on enrollment, three month, and three year gated SPECT perfusion studies. We can quantify the changes in magnitude of ischemic burden by treatment group using a simple linear regression model. We hypothesize that some will improve, some will worsen and some will show no change. If our evaluation of the data reveals a large group without change, we will consider a categorical analysis of the data. Additionally, we will control for interim non-protocol drug therapy. Comparing the enrollment study to the three year study will look at the ability of study drug to change ischemic burden by affecting atherosclerotic progression which is the primary endpoint of the substudy. Comparing the enrollment study to the three month study will look at direct effects of study drug on vascular tone and responsiveness.

New ECG changes in the absence of perfusion changes at the three month test will be analyzed by treatment group to examine the potential effects of drug therapy alone on ECG parameters. The initial stress perfusion image will also be compared with patient symptoms, and with angiographic findings at enrollment. The degree to which minor luminal narrowings can cause ischemic burden through functional or dynamic stenoses will be examined. Additionally, we will determine if abnormal perfusion scans at enrollment are predictive of future symptoms, angiographic findings, and outcomes. We will look at the ability of perfusion imaging to identify those women who benefit most from treatment in terms of ischemic burden, symptoms, and outcome.

Functional status and exercise duration may be affected by hormone replacement therapy. Enrollment treadmill tests will be compared to the those obtained at the three month and three year endpoint to look at the acute and chronic effects of drug therapy on exercise capacity. We will compare Bruce treadmill variables and estimated metabolic equivalents to responses on functional status questionnaires regarding activity levels in everyday life. Changes in functional status will be compared across treatment groups.

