18.8 DISCUSSION

Coronary artery disease is the number one cause of morbidity and mortality in women, however, the diagnosis of coronary disease in women is complicated. As many as 25-75% of women referred for evaluation of chest pain with insignificant disease will have either abnormal treadmill ECGs or abnormal perfusion imaging. This constellation of positive noninvasive testing with the presence of insignificant coronary disease may indicate dynamic functional stenoses (e.g., microvascular angina, or vasospastic angina), or may simply be false positive studies.

The overall outcome of this trial will be to characterize the ability of hormone replacement therapy and antioxidants to slow the progression of coronary artery disease as assessed by luminal diameter at catheterization. However, angiographic changes are often minimal in regression trials despite marked improvement in patient outcomes. This is due to difficulties in quantification of angiographic stenoses, to the development of more stable plaques, and potentially to the differences in vasomotor tone between normal and diseased vessels. A recent study looked at changes in nuclear perfusion imaging with short term fluvastatin therapy (cholesterol lowering agent). They found a 30% decrease in ischemic territory by perfusion imaging with a drug thought to improve vascular function and known to improve clinical outcome. The current substudy will characterize the effects of treatment on the patient's

ischemic burden with exercise nuclear perfusion imaging. Nuclear perfusion imaging will provide an additional method by which to quantify changes in coronary atherosclerosis and function, and to correlate changes in ischemia with improvements in luminal diameter and patient outcome.

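### The SPECT substudy's treatment comparison is to control for drugs taken after randomization, and Appendix E makes no as-randomized comparison primary, so the adjusted estimate can be biased in either direction

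*Protocol*

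**What the plan says.** The substudy's primary endpoint (section 18.2) is "To examine the chronic effect of study drug on changes in perfusion defect size (ischemic burden) from baseline to three year perfusion stress test". Section 18.6 gives the comparison: "We can quantify the changes in magnitude of ischemic burden by treatment group using a simple linear regression model". It allows a categorical analysis if many women show no change, and then adds: "Additionally, we will control for interim non-protocol drug therapy". Section 18.7 says the endpoint may instead be handled as dichotomous, combining progression with clinical events.

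Section 18.4 places the baseline image "within 7 days of randomization and prior to initiation of study drug". Therapy that is interim between that image and the three-month or three-year image is therefore, in practice, therapy taken after randomization.

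Appendix E does not say which result, adjusted or unadjusted, is the main one. The intention-to-treat statement in section 10.2.2 is made for the trial's primary MLD analysis and is not repeated for the substudy.

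**The concern.** Randomization makes the arms alike in everything that precedes treatment. It gives no such assurance for what follows. A covariate measured during follow-up can be shifted by treatment and can also mark how the woman's disease is going. If both are true, comparing women with the same interim drug use means comparing women who differ by arm in latent ischemia, and the treatment coefficient absorbs that difference. If the interim drug itself acts on ischemia, adjustment also removes the part of the treatment effect that runs through it.

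At stake is the substudy's main inference, the three-year effect of hormone therapy or antioxidants on perfusion defect size. A false signal or a distorted estimate could be reported with the authority of a randomized comparison.

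**Working it through.** The protocol gives no figure for this point, so there is none to reproduce. The check has two parts.

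**1. Does the protocol supply the links?**

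- *Treatment to drug use.* Section 8.4.1 manages hormone side effects with, among other things, "use of a mild diuretic for fluid retention". Section 4.1 reports of an earlier hormone trial that "all hormone regimens lowered LDL cholesterol levels"; that this would change lipid-drug prescribing is inference.
- *Drug use to outcome.* Section 18.8 says of a cholesterol-lowering drug: "They found a 30% decrease in ischemic territory by perfusion imaging with a drug thought to improve vascular function".
- *Ischemia to drug use.* That worsening ischemia or symptoms leads to new drugs is ordinary clinical reasoning; the protocol does not state it.
- *Masking.* Section 5 claims only: "This will increase the probability that all women will receive similar concomitant treatments, testing and evaluation during the conduct of the trial". It also expects side effects to lead some women or staff to presume an assignment.

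The links are plausible but not quantified.

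**2. What could adjustment do? (All inputs assumed.)**

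For each woman, T = 0 or 1 is the arm.

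- Latent change in ischemia: L = effect × T + noise, SD 4 points.
- Interim drug: logit P(D = 1) = a + 0.25 × L + g × T.
- Observed change: Y = L + residual, SD 4. The drug is inert unless stated.
- Women per arm: 180, which is 450 / 2 = 225 less 20% dropout (225 × 0.80 = 180). This assumes that nearly all trial women join the substudy.
- g = 0.5 is an odds ratio of e^0.5 = 1.65; g = 1 is e^1 = 2.7.

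Y is regressed on T alone, then on T and D. With a = -1, about 30% of controls take the drug; at g = 0.5 and g = 1 with no effect on ischemia, about 40% and 50% of the other arm do. Results hardly change with a = 0. Ranges below cover repeated runs.

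| True effect | g | T only | T and D |
|---|---|---|---|
| 0 | 0 | 0; 5% false positive | 0; 5% |
| 0 | 0.5 | 0; about 5% | -0.31 to -0.34; 8-9% |
| 0 | 1 | 0; about 5% | -0.64 to -0.70; 19-22% |
| +2 (worsening) | 0 | about 2.0; power 0.91 | 1.65 to 1.68; power 0.82 |
| -2 (benefit) | 0 | -2.0 | about -1.7 to -1.8 |
| -2 | 0.5 | -2.0 | -2.0 |
| -2 | 1 | -2.0 | -2.3 |
| 0, drug use unrelated to L | 1 | 0 | 0 |
| -2, drug use unrelated to L | 1 | -2.0 | -2.0 |

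If the drug lowers ischemia by 6 points and g = 0, a true -2 reduces drug use from about 30% to 22%. The total effect is then about -2 - 6 × (0.22 - 0.30) = -1.5. The unadjusted analysis gives -1.51 and the adjusted one -1.73.

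A second model with a different structure (outcome SD about 1.2, drug given when a noisy severity score passes a threshold, inert drug, no treatment effect) gives smaller distortions. Drug use falling from 36% to 29% gives an adjusted estimate of +0.06 (0.06 / 1.2 = 0.05 SD). A fall from 36% to 22% gives +0.12 (0.10 SD). The unadjusted estimate is 0 in both.

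So adjustment can create an effect, shrink one, enlarge one or leave it alone, depending on quantities the protocol does not give.

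**The case against.** The strongest reply is that the regression in section 18.6 is called simple and by treatment group, which read literally has treatment as its only predictor. The adjustment sentence opens with Additionally, so it may describe a supplementary analysis. That stands as a possible reading. The text does not settle it, and nothing in Appendix E puts the unadjusted result first.

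Second, the one drug path the protocol spells out, the diuretic, is for fluid retention. If its use is unrelated to ischemia and it does not act on ischemia, adjusting for it does no harm, as the table shows. This also stands: the bias needs drug use that depends on ischemia, and on treatment directly or through ischemia.

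Third, masking is meant to keep concomitant therapy similar, and nothing in the documents points to gaps as wide as 30% against 40% or 50%. That limits what can be said about size but does not remove the problem, because section 5 claims only a higher probability of similar care.

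Two stronger inferences are tempting and unsupported. A reader might conclude that adjustment always understates a real effect; the runs with a true -2 show estimates too small, correct and too large. A reader might also take this regression to be the only analysis planned for the endpoint; sections 18.6 and 18.7 also allow categorical or dichotomous analyses.

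Finally, the reach is small. Section 18.1 presents the substudy as a proposal likely to need outside funding, and section 7.2 lets women decline it.

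**Conclusion.** The point holds in limited form. Section 18.6 commits to controlling for a post-randomization variable in the substudy's treatment comparison, and Appendix E does not protect an as-randomized result. The adjusted estimate can be biased in either direction when treatment (directly or through ischemia) and latent ischemia both influence interim drug use. Under the assumed inputs the false-positive rate is about 8-9% with an odds ratio of 1.65 for drug use and 19-22% with 2.7, against 5% unadjusted. These are illustrations, not forecasts. With no effect of treatment on ischemia or on drug use, or with drug use unrelated to ischemia, there is no bias.

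This is worth correcting because the change is small and the conditions for bias cannot be ruled out in advance. It does not touch the trial's primary MLD analysis.

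**What to change.** In section 18.6, replace the adjustment sentence with wording to this effect: the main substudy analysis compares women as randomized, adjusted at most for drug therapy at baseline, before study drug starts; interim non-protocol drug use is reported by arm as a descriptive result; any analysis that conditions on interim drug use is exploratory and not a randomized comparison. The same rule should cover the categorical or dichotomous version if that is used.

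The cost is a sentence or two. Concurrent medications are already recorded at follow-up visits (Table 2 footnote; sections 7.4.3 and 7.4.4). Table 2 does not itemize drug therapy at entry, so if baseline adjustment is wanted, confirm that the entry forms record it.

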7.4.4 Annual Visits (at 12, 24, 36 months)

The participant will be asked to bring in all unused study medication and all other medications she has taken since the last study visit. At the 36 month visit, the participant will be asked to fast 12 hours before coming to the visit. During each annual visit, a designated individual will review and discuss any symptoms potentially attributable to either study medication. The coordinator or his/her designee will:

1. At the 36 month visit, draw fasting study bloods for processing and shipping to the central biochemistry laboratory. Feed participant if desired. At the 36 month visit (42 month for some women), obtain pre-angiogram bloods, if necessary;
2. Document any clinical outcomes that have occurred since the last visit and record current medications on a follow-up form;
3. Record study medication capsule/tablet count on follow-up form; dispense a new supply of study medication;

4. At the 12 and 36 month visits obtain an ECG;
5. Perform a breast examination, provide breast self-exam teaching, perform pelvic examination, obtain a Pap smear (if uterus present and none done within past 12 months) and complete the physical exam form;
6. Ask participant to sign a medical release. Make arrangements to obtain any mammogram report done within the past 12 months, or schedule a mammogram;
7. At the 36 month visit (42 month for some women), schedule the exit angiogram and the visit.
8. At the 36 month visit, perform appropriate assessments for patients in the Effects of Hormone Replacement Therapy on Electrocardiographic and Scintigraphic Measures of Myocardial Ischemia Study.

Comment [TBC2]:

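### The SPECT substudy credits its enrollment-to-three-year change to atherosclerotic progression, but an off-drug to on-drug comparison gives only a total effect (tone plus progression)

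*Protocol*

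**What the plan says.** Section 18.2 defines the substudy's primary endpoint as the chronic effect of study drug on perfusion defect size between the baseline and three-year scans. It names no mechanism.

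Section 18.6 supplies one. For the three-year comparison: "Comparing the enrollment study to the three year study will look at the ability of study drug to change ischemic burden by affecting atherosclerotic progression". For the three-month comparison: "Comparing the enrollment study to the three month study will look at direct effects of study drug on vascular tone and responsiveness". The last paragraph of Section 18.8 repeats the split, reading the three-month test as vasomotor tone and the three-year test as disease progression.

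On scan timing, Section 18.4 says:
- Enrollment: "Women will undergo exercise gated SPECT imaging within 7 days of randomization and prior to initiation of study drug".
- Three months: "For those women who had perfusion defects initially, a follow up gated SPECT perfusion image will also be obtained at this time point". Women with a negative enrollment scan have only the exercise ECG at that point.
- Three years: "At completion of the protocol and prior to 3 year recatheterization, all women will undergo repeat Bruce treadmill testing and gated SPECT perfusion imaging".

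Section 7.4.4 puts the last assessment at a named visit: "At the 36 month visit, perform appropriate assessments for patients in the Effects of Hormone Replacement Therapy". Its list for the annual visits (12, 24 and 36 months) also includes: "Record study medication capsule/tablet count on follow-up form; dispense a new supply of study medication".

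**The concern.** The three-month and three-year comparisons start from the same off-drug scan and use the same measure, ischemic burden. If the scan responds to vascular tone at three months, it can also respond to tone at three years in women still taking the drug. Section 18.6 nevertheless reads the first comparison as tone and the second as progression, and gives no reason why the tone component should have disappeared.

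The substudy's primary conclusion is at stake. A drug that altered only vascular tone, with no effect on the disease, could be reported as having slowed coronary atherosclerosis. The main trial's MLD endpoint is not affected.

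**Working it through.** **Step 1. Drug status at each scan.**

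| Scan | Drug status | Source |
|---|---|---|
| Enrollment | Off drug | Section 18.4 |
| Three months | On drug | Section 18.4; Table 2 (3M) |
| Three years | On drug, by the schedule | Section 7.4.4 and Table 2 place it at 36 months. Table 2 shows dispensing through 30 months and an adherence assessment at 36. Section 7.4.4 lists a count and a new supply at annual visits |

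No washout or off-drug scan appears anywhere after enrollment.

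**Step 2. What each contrast contains.** Let T3 and T36 be the between-arm differences due to vascular tone at 3 and 36 months, and P3 and P36 those due to progression. Both are zero at enrollment.

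- Enrollment to three months: T3 + P3 (P3 presumably small)
- Enrollment to three years: T36 + P36
- Three months to three years: (T36 − T3) + (P36 − P3)

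The second line equals P36 only if T36 = 0. Section 18.6 needs that condition and does not state it. Section 2.3.3 points the other way for estrogen, describing both acute and chronic exposure as effective on vascular tone. The third line removes tone only if T36 = T3, and it omits P3.

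**Step 3. Illustration in percentage terms.** Section 18.8 cites a short-term study of a cholesterol-lowering drug: "They found a 30% decrease in ischemic territory by perfusion imaging with a drug thought to improve vascular function". Suppose, purely as an assumption, that a study drug had T3 = T36 = −30 and P3 = P36 = 0.

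- Enrollment to three years: −30 + 0 = −30, none of it progression
- Three months to three years: (−30 + 30) + 0 = 0

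If tone instead waned to T36 = −15, still with no progression effect:

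- Enrollment to three years: −15
- Three months to three years: −15 + 30 = +15, a spurious worsening

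So the second contrast is not clean either.

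**Step 4. Illustration in terms of significance.** The protocol gives no SD for defect size, so the persisting tone effect d is in assumed SD units, with no effect on progression. For a two-sided 0.05 normal test with n per arm:

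P(significant) = Φ(d√(n/2) − 1.96) + Φ(−d√(n/2) − 1.96)

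Section 18.7 uses n = 225 per arm, so √(n/2) = 10.61. With an assumed 20% loss, n = 180 and √(n/2) = 9.49. For d = 0.2 and n = 225, the first term is Φ(2.12 − 1.96) = Φ(0.16) = 0.56 and the second is negligible.

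| d (SD) | n = 225 | n = 180 |
|---|---|---|
| 0 | 0.05 | 0.05 |
| 0.1 | 0.19 | 0.16 |
| 0.2 | 0.56 | 0.48 |
| 0.3 | 0.89 | 0.81 |
| 0.4 | 0.99 | 0.97 |

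These are chances of a significant three-year result when nothing has happened to progression. They show how the problem scales with d and do not estimate d. No figure stated in the protocol is at issue.

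**The case against.** **The trial is randomized and placebo-controlled.** This stands as far as it goes. The three-year between-arm difference is a valid effect of the drug on ischemic burden. Randomization does not divide that effect between tone and structure when active-arm women are scanned on active drug.

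**The endpoint is not misdefined.** This stands. A reader might infer that the primary endpoint itself is wrong, but Section 18.2 speaks only of a chronic effect and is sound as a total effect. The fault is confined to the interpretation in Sections 18.6 and 18.8.

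**The substudy already recognizes function as well as structure.** This partly stands. Section 18.6 opens with acute and chronic effects on tone, Section 18.8 mentions both atherosclerosis and function, and the three-month tone result and MLD would be available alongside. No planned analysis combines them, however, and the progression reading is still attached to the three-year comparison.

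**The size is not established.** This stands. A reader might infer that about 30% of baseline defect size would be misattributed. The documents do not support that: the figure concerns another drug, no comparator or persistence is given, and the effect is not said to be purely tone. Section 2.3.3 supports persistence for estrogen only and reports conflicting results when progestin is added, which is what women with a uterus receive (Section 4.1). Nothing is stated about a persisting tone effect of the antioxidants.

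**On-drug status at three years is inferred.** This is fair. Section 18.4 places the scan loosely at the end of the protocol, and Table 2 marks no dispensing at 36 months although Section 7.4.4 lists it for annual visits. Even so, drug dispensed at 30 months and counted at 36 points to an on-drug scan.

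**The angiograms have standardized vasodilator use (Section 12.2.9) and the scans do not.** A reader might infer that the substudy has no control of tone at all. That is too firm, because the documents disagree on the stress method: Table 2 and the contents list name dipyridamole, while Section 18.4 describes Bruce treadmill exercise. The point here does not depend on it.

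**Conclusion.** The concern holds as a fault of interpretation. The enrollment-to-three-year comparison measures the total drug effect on ischemic burden, and Sections 18.6 and 18.8 are not entitled to assign it to atherosclerotic progression. This rests on the three-year scan being on drug, as the visit schedule indicates, and on the protocol's own premise that the scan detects vascular tone.

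The size of any misattribution cannot be derived from the documents. It is zero if the tone effect has gone by 36 months and equals the whole observed difference if there is no progression effect.

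A reader might also infer that the three-month-to-three-year change should replace the three-year comparison as the measure of progression. The documents do not support that. It depends on a stable tone effect after three months, misses earlier progression, and excludes women who start without a defect and later develop one. Its place is supportive.

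The correction is worth making because it changes what the substudy may conclude, but it concerns an optional substudy and leaves the trial's primary hypotheses untouched.

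**What to change.** 1. In Sections 18.6 and 18.8, describe the enrollment-to-three-year comparison as the total effect of study drug on ischemic burden (vascular tone plus progression), and state that no progression effect will be claimed from it alone. Leave Section 18.2 as it is.
2. Add to Section 18.6 a supportive analysis: the three-month-to-three-year change, compared by randomized arm, in women with a perfusion defect at enrollment. They already receive all three scans, and the subset is defined by a scan taken before drug starts, so the arms remain comparable by randomization.
3. State the limits of that analysis: it reflects progression only if the tone effect is stable after three months; it misses progression before then; and it leaves out women who begin without a defect and develop one.
4. While editing, reconcile Section 18.6, which has every woman's defect size quantified at three months, with Section 18.4, which gives that scan only to women with an enrollment defect.

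The cost is a few sentences and one further contrast on scans already planned. The supportive analysis is less precise and answers the question in a narrower population.
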